## **13. Analysis of Primary Efficacy Endpoint**

The primary analysis will be based on the ITT Population. The null hypothesis of no difference in proportion of subjects who reach success (clinical status not worse than the clinical status category at Baseline at Day 7) in two treatment groups will be tested versus the alternative hypothesis that there is a difference between proportions of subjects who reach success in two groups. Hypothesis testing will be performed using Cochran-Mantel-Haenszel (CMH) stratified by age category ( $\leq 65$  versus  $> 65$ ) at a two-sided 0.05 significance level. The difference in proportions between two groups with standard deviation, and 95% Miettinen-Nurminen (1985) confidence interval (CI) will also be provided.

If the CMH fails the Mantel-Fleiss criteria (1980), a chi-squared test will be the basis of evaluation and unweighted asymptotic CIs for the difference in proportions will be used. If, when implementing a chi-squared test, an expected cell count  $< 5$ , Fisher's exact test will be used and exact (Santner-Snell, 1980) CIs will be provided.

For subjects with clinical status assessment at Baseline (Day 1), missing data at Day 7 will be imputed based on the method described in Section 4.1. Subjects with missing data at Baseline (Day 1) will be imputed as failure.

Subjects who use prohibited medication (medications being administered as part of other experimental studies or the use of experimental non-IVIG products, COVID-19 convalescent plasma, or interferons) on or before Day 7 will be counted as failure. Prohibited medications will be identified during blinded review described in Section 7.

Shifts from Baseline (Day 1) at Day 7 in terms of the 6-point clinical status scale will be reported (descriptive analysis).

The durability of the treatment effect will be reviewed based on the comparison of proportions who are stabilized or improved between treatment arms at Day 14, Day 21, and Day 33 in the final analysis. No formal hypothesis testing will be conducted for the Day 21 and Day 33 analyses and the descriptive comparison will be carried out based on the method applied for the primary analysis. Graphical representations of clinical status, and changes from baseline, over time will be presented by treatment group.

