#### 2.1.1 Primary Endpoints

- Proportion of subjects with stabilized or improved clinical status at Day 7 on at least one category on a 6-point clinical status scale.
- Change from Baseline (Day 1) at Day 7 in terms of the 6-point clinical status scale (descriptive analysis).

Clinical status categories will be defined as:

1. Hospital discharge or meet discharge criteria (discharge criteria are defined as clinical recovery, i.e., no fever, respiratory rate, oxygen saturation return to normal, and cough relief).
2. Hospitalization, not requiring supplemental oxygen.
3. Hospitalization, requiring supplemental oxygen (but not non-invasive mechanical ventilation (NIV)/high-flow nasal cannula [HFNC]) as defined by A-a Gradient < 150 mmHg.
4. Intensive Care Unit (ICU)/hospitalization, requiring NIV/HFNC therapy, as defined by A-a Gradient  $\geq$  150 mmHg.
5. ICU, requiring extracorporeal membrane oxygenation (ECMO) and/or IMV.
6. Death.

A subject meets the success criteria of stabilization or improvement if the clinical status category on Day 7 is not worse than the clinical status category at Baseline (Day 1 prior to IMP infusion).

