#### **4. General Analytic Considerations**

Unless otherwise mentioned:

- Number of subjects in the defined population and number of subjects with available data will be provided.
- Continuous variables will be summarized using descriptive statistics such as mean, standard deviation, median, quartiles, minimum, and maximum, and 95% confidence interval.
- Categorical variables (e.g., gender, race, etc.) will be provided using frequency tabulations.
- Individual listings will be provided to support the descriptive analyses.
- Baseline is defined as the last observation prior to randomization for the analysis of efficacy endpoints. Baseline is defined as the last observation prior to first administration of study drug for the analysis of safety endpoints.

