#### **4.3 Covariate Adjustment**

Testing will be stratified by age category ( $\leq 65$  versus  $> 65$ ).

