### **Sensitivity Analysis**

The primary endpoint analysis will be repeated using the PP and Safety Populations as sensitivity analyses.

A complete case analysis, using patients with completed clinical status assessments at Day 7, will be presented.

An analysis of the primary endpoint, using all data collected regardless of prohibited medication use, will also be conducted.

A worst-case scenario will be conducted as an additional sensitivity analysis, counting all subjects with missing data at Baseline (Day 1) or Day 7 as failures.

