#### 14. Analysis of Secondary Endpoints

The analyses for secondary endpoints will be based on the ITT Population. The hypothesis testing with p-value assessments for secondary endpoints at designated timepoints will be implemented for confirmatory purpose after statistical significance is claimed from the primary endpoint. The following secondary endpoints will be analyzed by hierarchical procedure in the order specified below with overall 2-sided type I error of 0.05:

1. Length of hospital stay (time to discharge) through Day 33
2. Proportion of subjects with maintenance or improvement by at least one category on the 6-point clinical status scale on Day 14.
3. Cumulative duration of IMV through Day 33
4. Proportion of subjects with severe progression defined as requiring ECMO, IMV and/or have died through Day 33
5. Length of time in ICU from randomization through Day 33
6. Mortality rate through Day 33

The hierarchical testing procedure will stop when one of the endpoints cannot demonstrate statistical significance, i.e. as soon as the first statistical test yields a p-value  $\geq 0.05$ . If this happens, the subsequent endpoints will not be tested.

Length of hospitalization is defined as (date of discharge – randomization date + 1). Subjects who are still hospitalized as of Day 33, subjects with missing end dates due to withdrawal, subjects with unusable end dates due to prohibited medication use, or those who died on/prior to Day 33 will be censored at Day 33. The median time to discharge and associated 95% CI for each treatment arm will be estimated using the Kaplan-Meier method. Comparisons between treatment arms will be performed using a log-rank test, stratified by age category. A rate ratio and associated 95% CI, equivalent to a hazard ratio from a Cox proportional hazard model stratified by age, will also be presented.

Proportion of subjects that stabilized or improved at Day 14 is defined as per the primary endpoint and hypothesis testing for proportions will be conducted as described for the in the primary endpoint section.

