Cumulative duration on IMV through Day 33 and is defined as (IMV end date – IMV start date + 1). Subjects who do not require IMV will have a duration set to 0. Subjects who die on or prior to Day 33 or are still on IMV at Day 33, will have a duration set to their actual/projected Day 33 date for the IMV end date, so long as prohibited medication was not administered. If IMV end date is missing but subject is discharged from ICU or hospital, then IMV end date will be set to the earlier of the ICU or hospital discharge date. Otherwise, subjects without usable IMV end date information due to withdrawal or prohibited medication use will use a projected Day 33 date for the IMV end date. Comparisons between

treatment arms will be performed using a stratified Wilcoxon-Mann-Whitney (van Elteren) test with age category as a stratification factor.

Proportion of subjects with severe progression will be defined as the proportion that require ECMO, IMV or died prior to Day 33. For this analysis, subjects who use prohibited medication prior to the earliest of progression or Day 33 will not be included in analyses. Hypothesis testing for this endpoint will be conducted as described for the primary endpoint.

Length of time in ICU from randomization through Day 33 includes number of days spent in the ICU from randomization through Day 33 and is defined as [ICU discharge date – (later of ICU admittance date, randomization date) + 1]. Subjects who are not admitted to the ICU will have a duration set to 0. Subjects who die on or prior to Day 33 or are still in the ICU at Day 33, will have a duration set to their actual/projected Day 33 date for the discharge date, so long as prohibited medication was not administered. If ICU discharge date is missing but subject is discharged from hospital, then ICU discharge date will be set to hospital discharge date. Otherwise, subjects without usable ICU end date information due to withdrawal or prohibited medication use will use a projected Day 33 date for the ICU end date. Comparisons between treatment arms will be performed using a stratified Wilcoxon-Mann-Whitney (van Elteren) test with age category and baseline ICU status (In ICU at baseline versus not in ICU at baseline) as stratification factors.

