Mortality rate is defined as the proportion of subjects who have died on or prior to Day 33. For this analysis, subjects who use prohibited medication prior to the earliest of death or Day 33 will not be included in analyses. Hypothesis testing will be performed as described for the primary endpoint.

Key secondary endpoints which demonstrate statistical significance will be analyzed by subgroups including sex (male/female), race, ethnicity, geographic region, and disease severity (according to the definitions in the eCRF). All key secondary endpoints will be analyzed by age using testing analogous (unstratified) testing methodology to the specified analyses. Length of time in ICU from randomization through Day 33 will also be analyzed by baseline ICU status. Sensitivity analyses, using all available data, regardless of prohibited medication usage, will be conducted where applicable. The descriptive analyses for the following other secondary endpoints will be based on the primary efficacy analysis (e.g. CMH) method:

- Proportion of patients whose results of reverse transcription polymerase chain reaction (RT-PCR) for SARS-CoV-2 from nares/throat swab and/or sputum and/or lower respiratory tract sample are “Not Detected” on Day 7
- Proportion of subjects admitted to the ICU from randomization through Day 33
  - Only admittance (new or returning) post-randomization will qualify as an event
  - Analyses will be stratified additionally by baseline ICU status
  - If expected event counts do not satisfy CMH testing criteria, baseline ICU status will be removed from analysis as a first step in analysis update
- Proportion of subjects with improvement on Days 7, 14, 21, 33

- Proportion of subjects requiring IMV by Day 33.

The descriptive analyses for the following, other secondary endpoints will be based on the Kaplan-Meier analysis of length of hospitalization:

- Time to recovery through Day 33 where recovery is defined as a clinical status of 1 or 2
- Time to first improvement in clinical status through Day 33

These secondary endpoints will also be analyzed by age category.

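### The primary and Day 14 tests stratify by age alone although success is judged against baseline clinical status; adding that stratum is a cheap gain in efficiency, not the repair of an error

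*SAP*

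**What the plan says.** SAP 13 tests the primary endpoint as follows: "Hypothesis testing will be performed using Cochran-Mantel-Haenszel (CMH) stratified by age category". Protocol 9.2.3.2 has the same sentence. SAP 4.3 is the only general rule on covariates and names nothing else: "Testing will be stratified by age category". SAP 14 carries the test over to Day 14, second in the key secondary hierarchy: "hypothesis testing for proportions will be conducted as described for the in the primary endpoint section".

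SAP 2.1.1 counts a subject as a success if "the clinical status category on Day 7 is not worse than the clinical status category at Baseline". The sensitivity analyses in SAP 13 change the population ("The primary endpoint analysis will be repeated using the PP and Safety Populations as sensitivity analyses"), the handling of missing data, or the handling of prohibited medication. None adjusts for baseline status. SAP 13 also describes shifts from baseline to Day 7. Disease severity is a subgroup in the protocol synopsis and, after a significant result, in SAP 19. Randomisation is blocked within site only (Protocol 9.3).

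For the ICU endpoints the plan does use baseline status. ICU length of stay is tested "with age category and baseline ICU status (In ICU at baseline versus not in ICU at baseline) as stratification factors". ICU admission is also stratified by baseline ICU status, with a rule if the CMH criteria are not met: "baseline ICU status will be removed from analysis as a first step in analysis update".

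**The concern.** Eligibility requires supplemental oxygen and excludes invasive ventilation, so nearly all subjects should start in category 3 or 4. From category 3, a subject fails on reaching 4, 5 or 6. From category 4, only 5 or 6 is a failure. The starting category therefore enters the definition of the outcome and may well predict it, although the documents do not say how strongly or in which direction.

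If it does predict success, a test stratified by age alone leaves that variation unexplained. The estimated difference is also not adjusted for a chance imbalance in starting category, which site-blocked randomisation does nothing to limit. The primary test is the gate to all six key secondary endpoints, so lost power there is passed on. An adjusted analysis first proposed after unblinding would be post hoc and open to dispute.

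**Working it through.** **The plan's own figure.** Inputs from Protocol 9.1: success 0.60 and 0.80, two-sided 0.05, 88 per arm, 15% drop-out. With pooled null variance:

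z = [0.20·√88 − 1.96·√(2·0.7·0.3)] / √(0.6·0.4 + 0.8·0.2) = (1.876 − 1.270)/0.632 = 0.958, so power is 83.1%.

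At 104 per arm, z = (2.040 − 1.270)/0.632 = 1.217 and power is 88.8%. 88/0.85 = 103.5, rounded up to 104 per arm, or 208. The stated power of at least 80% is reproduced.

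**The test.** In stratum h, with n₁ active and n₀ placebo subjects, N = n₁ + n₀ and X successes in total, E = n₁X/N and V = n₁n₀X(N − X)/[N²(N − 1)]. The CMH statistic is [Σ(x₁ − E)]²/ΣV, compared with 3.841.

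**Effect of adding baseline status.** 20,000 simulated trials per scenario, overall success held at 0.60 and 0.80. Assumptions not in the documents: 30% aged over 65, age log odds ratio −0.5, category-4 share 30%, 50% or 70%, and the odds ratio (OR) for success in category 4 versus 3. Power is shown for a 50% share; the change covers all three shares. N=208 is included because imputation brings every randomised subject into the ITT test.

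| OR | N=176, age → age × status | Change (points) | N=208, age → age × status | Change (points) |
|---|---|---|---|---|
| 1 | 83.4% → 83.0% | −0.4 to −0.6 | 89.0% → 88.8% | −0.2 to −0.3 |
| 2 | 83.7% → 84.0% | +0.2 to +0.5 | 89.1% → 89.4% | +0.1 to +0.3 |
| 4 | 83.7% → 86.2% | +1.7 to +2.6 | 89.4% → 91.8% | +1.5 to +2.4 |
| 8 | 83.0% → 89.1% | +3.5 to +6.2 | 89.3% → 93.9% | +3.0 to +4.8 |

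The standard error of one power estimate is about √(0.89·0.11/20,000) = 0.2 points, so the entries for OR 1 and 2 amount to little or no change. Type I error (0.70 in both arms) was 4.7–5.1% for both tests. The Mantel-Fleiss criterion was met in every simulated trial.

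**Second check.** A separate simulation with 60,000 trials per scenario, age OR 0.5 and status split 50/50 or 70/30 gave −0.3 to −0.5 points at OR 1, +0.2 to +0.4 at OR 2, +1.5 to +2.8 at OR 4 (either direction) and +2.7 to +5.5 at OR 8. At 88 per arm and a 50/50 split, the gain equals about 8% (OR 4) or 18% (OR 8) more subjects.

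**Chance imbalance.** With half the subjects in each category and 104 per arm, the between-arm difference in share has SD √(2·0.25/104) = 6.9 points. Averaged over the arms, success differs between categories by 0.137, 0.262 and 0.366 at OR 2, 4 and 8. A 1-SD imbalance therefore moves the estimated difference by 0.9, 1.8 or 2.5 points. The test's 5% error rate already allows for this.

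**Missing baseline.** SAP 13 counts these subjects as failures. In a stratum of their own, X = 0, so E = 0 and V = 0. They drop out of the test and the failure imputation is undone. With 5% missing (assumed), N=208 and OR 4, power is 83.5% for age only, 85.8% with the stratum taken from Screening status, and 90.2% with a separate missing stratum. That last 4.4 points comes only from losing the imputed failures.

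**The case against.** The strongest reply is that nothing is broken. The age-only test holds its level, meets its stated power, and one pre-specified prognostic stratum is a legitimate choice. The benefit rests on an unknown. Break-even is at an odds ratio of about 1.5, and gains above 2 points need about 4, which at a 50:50 mix means placebo success of 44% in one category and 76% in the other. Category 4 subjects have fewer ways to fail but are sicker, and the two may offset each other. The ICU precedent is also imperfect, because baseline ICU status bears more directly on ICU days and ICU admission. All of this stands. It limits the point to a recommendation and leaves the size of the gain open.

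Other objections carry less weight. By-arm reviews for the data monitoring committee have taken place, but SAP 8 describes them as safety reviews with unblinded data going to the committee only; a change made blind and documented is defensible. An amendment has a procedural cost, but the change is one of wording. Categories 3 and 4 are tied to the A-a gradient, which Protocol 7.2.4 schedules on Day 1 and Day 7 and not at Screening. Clinical status itself is recorded at Screening, however, and the gap affects only subjects without a Day 1 value. When Day 1 status is missing, the last pre-randomisation value is already the Screening value, so the two rules overlap harmlessly.

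**Conclusion.** The point holds as an efficiency improvement that should be made, not as a correction. The planned tests are valid and the sample size statement is right. Adding baseline status costs roughly half a point of power if it is not prognostic, is close to neutral at an odds ratio of 2, and gains about 1.5 to 3 points at 4 and about 3 to 6 points at 8. It also adjusts the estimate for chance imbalance. These sizes depend on assumed odds ratios, category shares and age effects. Varying the age share (15%, 40%) and age log odds ratio (0, −1) at N=208 kept the same pattern: −0.3 to −0.4, +0.4 to +0.5, +2.0 to +2.5 and +4.1 to +4.7 points at OR 1, 2, 4 and 8.

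**What to change.** Before unblinding, amend SAP 4.3, SAP 13 and Protocol 9.2.3.2 together:

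1. Stratify the primary and Day 14 CMH tests by age category × baseline clinical status (3 or lower versus 4 or higher), and report a Miettinen-Nurminen interval stratified in the same way.
2. Take the stratum from the last value before randomisation, in line with SAP 4: "Baseline is defined as the last observation prior to randomization for the analysis of efficacy endpoints". Protocol 6.1.2 allows condition to change between randomisation and dosing, so reconcile this with the pre-infusion Day 1 baseline in SAP 2.1.1.
3. For subjects with no Day 1 status, use the Screening clinical status for the stratum and keep them as failures. Do not create a missing stratum.
4. If the Mantel-Fleiss criterion fails, remove baseline status first, as SAP 14 does for ICU status, then follow the existing fallback in SAP 13.

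No change for site or region is needed. The cost is wording, or an entry in SAP 20 if the protocol is not amended. Status is already collected at Screening and Day 1. The downside is about half a point of power if baseline status turns out not to matter.

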11. Subjects who received COVID-19 convalescent plasma, IVIG products, anti-interleukin agents (eg, Tocilizumab), or interferons for their COVID-19 disease before enrolment or plan to receive this treatment during the course of the study.
12. Enrolled in other experimental interventional studies or taking experimental medications (ie, convalescent plasma). Diagnostic studies can be allowed if the anticipated total blood volume to be drawn across both studies and for therapeutic purposes does not exceed 450 mL over any 8-week period.

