4.2 Prior and Concomitant Therapy

Concomitant medication includes all pharmaceutical agents, vitamins, nutritional supplements, and herbal medicines used by the subject with the exception of *Octagam 10%* or placebo. Details on medications taken within 1 week prior to Screening and any concomitant medications taken during the study must be recorded in the electronic Case Report Form (eCRF). This includes off-label use of any drugs, devices, or interventions that have been used to manage COVID-19. Use of antivirals

(eg, remdesivir), corticosteroids, chloroquine or hydroxychloroquine, antibiotics, anticoagulants, or antiplatelet agents is allowed and must be documented in eCRF.

The use of medications being administered as part of other experimental studies or the use of experimental non-IVIG products, COVID-19 convalescent plasma, or interferons are forbidden. Should a circumstance arise where it is considered to be in the best interests of a subject to administer such a product, the subject should not receive further study infusions (*Octagam 10%* or placebo) if these are still ongoing. The other medications administered should be documented as concomitant medications, and the subject should continue to be followed up per protocol.

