For any withdrawals after study entry, the Investigator will obtain all the required details and document the reason(s) for discontinuation. If the reason for withdrawal of a subject is an AE, the main specific event or laboratory test will be recorded, and the Investigator will make thorough efforts to clearly document the outcome.

Other reasons for premature termination of subjects may be:

- Withdrawal of subject's consent.
- Pregnant and lactating subjects will be immediately excluded from the study.
- Investigator's opinion that the subject may be severely harmed if he/she continues study participation, namely by the treatment and procedures requested by the study protocol.
- Occurrence of a condition or disease that interferes with the study treatment or represents an exclusion criterion.
- Administration of IVIG other than *Octagam 10%*.
- Subjects do not comply with the study protocol.

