9.2.3.2 Primary and Secondary Endpoints

The ITT set will be used as the primary analysis set to analyze the primary endpoint. The handling of missing data is described in later section. A subject is determined to be a success if the clinical status category on Day 7 is not worse than the clinical status category at Baseline (Day 1, prior to IMP infusion). Subjects who use prohibited

concomitant medication (medications being administered as part of other experimental studies or the use of experimental non-IVIG products, such as COVID-19 convalescent plasma, or interferons) prior to the Day 7 clinical status assessment will be counted as failure.

A sensitivity analysis using all available data, regardless of prohibited medication usage, will be conducted.

The null hypothesis of no difference in proportion of subjects who reach success (clinical status not worse than the clinical status category at Baseline at Day 7) in two treatment groups will be tested versus the alternative hypothesis that there is a difference between proportions of subjects who reach success in two groups. Hypothesis testing will be performed using Cochran-Mantel-Haenszel (CMH) stratified by age category (≤ 65 versus > 65) at a two-sided 0.05 significance level. The difference in proportions between the two groups with standard deviation, and 95% Miettinen-Nurminen CI will also be provided.

The durability of the treatment effect will be reviewed based on the comparison between treatment arms of proportions who are stabilized or improved at Day 14, Day 21 and Day 33 in the final analysis. No formal hypothesis testing will be made for the Day 21 and Day 33 analyses and the comparison will be carried out by difference of proportions, standard error and 95% CI of the difference of proportions between two treatment groups.

The analysis for secondary endpoints will be based on the ITT population. The hypothesis testing with p-value assessments for key secondary endpoints will be implemented for confirmatory purpose after statistical significance is claimed from the primary endpoint. The following key secondary endpoints will be analyzed by hierarchical procedure in the order specified below with overall two-sided type I error of 0.05:

1. Length of hospital stay (time to discharge) through Day 33
2. Proportion of subjects with stabilized or improved clinical status of at least one category on the 6-point clinical status scale on Day 14.
3. Cumulative duration of IMV through Day 33

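### The prohibited-medication failure rule leaves out non-study IVIG and does not name anti-interleukin agents, so Day 7 and Day 14 scoring after such use is wrong-footed or undetermined.

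*SAP*

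**What the plan says.** Four places in the protocol and one in the SAP deal with non-study COVID-19 treatment, and they do not use the same list.

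- **Protocol 4.1.2, exclusion 11** gives as grounds for ineligibility: "COVID-19 convalescent plasma, IVIG products, anti-interleukin agents (eg, Tocilizumab), or interferons for their COVID-19 disease before enrolment or plan to receive this treatment". The planned use it means is use while on study.
- **Protocol 4.2**, which governs on-study use, says that medications from other experimental studies and "use of experimental non-IVIG products, COVID-19 convalescent plasma, or interferons are forbidden". After such use, study infusions stop but "the subject should continue to be followed up per protocol". The same section requires off-label COVID-19 treatments to be recorded, and it allows antivirals and corticosteroids.
- **Protocol 4.3.1** gives "Administration of IVIG other than" the study product as a possible reason for premature termination. It attaches no endpoint consequence.
- **Protocol 9.2.3.2** counts as failures subjects using other-study medications or "experimental non-IVIG products, such as COVID-19 convalescent plasma, or interferons) prior to the Day 7 clinical status assessment will be counted as failure".
- **SAP 13** has the same rule without the open-ended phrasing: "the use of experimental non-IVIG products, COVID-19 convalescent plasma, or interferons) on or before Day 7 will be counted as failure". It leaves the identification of prohibited medications to the blinded review in SAP 7. SAP 20 declares no change from the protocol.

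**The concern.** The plan's strategy for the primary endpoint is that use of a competing treatment before the Day 7 assessment is a failure. The list that triggers this omits two of the four classes in exclusion 11. One of them, IVIG, is the drug class under test. A placebo subject given commercial IVIG is directly contaminated control data, yet the failure rule as worded does not reach that subject.

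The same term (prohibited medication) also drives the Day 14 endpoint, the rule that a discharge after such use is not an event, the extrapolation of ICU and IMV end dates to Day 33, and exclusion from the severe-progression and mortality analyses. A gap in the list therefore reaches beyond the primary endpoint, although not in the same way for each endpoint.

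**Working it through.** **1. Compare the lists by class.**

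| Class | Exclusion 11 (prior or planned use) | Protocol 4.2 (on study) | Failure rule (Protocol 9.2.3.2, SAP 13) |
|---|---|---|---|
| Convalescent plasma | named | named | named |
| Interferons | named | named | named |
| Anti-interleukin agents | named | not named | not named |
| Non-study IVIG | named | outside the non-IVIG category | outside the non-IVIG category |

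Non-study IVIG would be caught only if given as part of another experimental study. An anti-interleukin agent might be classed as an experimental non-IVIG product. The open-ended phrasing in Protocol 9.2.3.2 makes that easier than the SAP wording does.

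**2. Follow a subject given non-study IVIG.**

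- If the subject stays in follow-up, the observed Day 7 status is used. Not worse than baseline is a success.
- If the subject is withdrawn under Protocol 4.3.1 after a post-baseline assessment, Protocol 9.2.5 and SAP 4.1 carry the last status forward, replaced by a worse status if death, ECMO/IMV or ICU data show one. Not worse than baseline is again a success.
- SAP 4.1 imputes failure only when there is no post-baseline assessment or there is prohibited medication use, and the list does not make this use prohibited.

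Day 14 follows the same route.

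**3. Reproduce the design figure.** Inputs from Protocol 9.1: 60% vs 80%, two-sided 0.05, 88 per arm, 15% drop-out. With p̄ the mean of the two rates:

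power = Φ{ [ (p₂ − p₁) − 1.96·√(2p̄(1−p̄)/n) ] / √( [p₁(1−p₁) + p₂(1−p₂)]/n ) }

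At n = 88, p̄ = 0.70: (0.20 − 1.96 × 0.0691)/0.0674 = 0.958, so power is 83.1%. The stated minimum of 80% holds. 88/0.85 = 103.5, giving 104 per arm and 208 in total, as stated.

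**4. Illustrate the effect.** The documents give no rate of such rescue. Assume that 60% and 80% are the rates when every class in exclusion 11 counts as failure, then add uncounted rescue scored as success. Results are shown at 88 per arm (the planning number) and at 104, because the ITT analysis imputes missing Day 7 data and so can use everyone randomized.

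| Assumed success, placebo vs IVIG | Difference | Power, n = 88 | Power, n = 104 |
|---|---|---|---|
| 60% vs 80% (none) | 20 points | 83.1% | 88.8% |
| 63% vs 80.5% | 17.5 | 73.6% | 80.5% |
| 65% vs 81% | 16 | 66.9% | 74.2% |
| 68% vs 82% | 14 | 57.4% | 64.7% |
| 62.5% vs 82.5% (equal) | 20 | 85.0% | 90.4% |
| 70% vs 90% (equal) | 20 | 91.9% | 95.5% |
| 62.5% vs 85% (more on IVIG) | 22.5 | 93.1% | 96.3% |
| 65% vs 90% (more on IVIG) | 25 | 98.2% | 99.3% |

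For 65% vs 81% at n = 88: p̄ = 0.73, (0.16 − 1.96 × 0.0669)/0.0658 = 0.438, so power is 66.9%.

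**5. Check the key secondary endpoints separately.** For discharge, ICU and IMV, an unlisted agent leaves later dates usable, so a discharge or end date after rescue counts. For severe progression and mortality, Protocol 9.2.3.2 and SAP 14 remove prohibited-medication users from the analysis. There an unlisted agent keeps the subject in, with any death or progression counted.

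**The case against.** Exclusion 11 is an eligibility criterion and covers prior or planned use. Unplanned on-study use falls under Protocol 4.2, and the SAP names the same classes as that section. A reader might infer that the SAP departs from the protocol's on-study rule. It does not: the inconsistency lies within the protocol and the SAP inherits it. Other active treatments are allowed without being failures, so how to score an unlisted agent is partly an estimand choice. This stands, but that choice has to be written down, and for IVIG the present wording looks like an oversight.

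A reader might infer that a subject given an anti-interleukin agent is certain to be scored as a success. The documents do not support that, because blinded review could classify the agent as prohibited and must document its decisions before unblinding. The outcome is undetermined.

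A reader might also infer that the gap necessarily weakens the trial, or that rescued subjects become successes on every key secondary endpoint. The first depends on which arm has more rescue, which the documents do not give. The second is wrong for severe progression and mortality, as step 5 shows.

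Some protection exists. Subjects who have worsened by Day 7 fail whatever they received. The worst-case and complete-case analyses in SAP 13 bear on the withdrawal route, and the per-protocol set may drop such subjects if the use is judged a major deviation. None of these changes the primary ITT result. The planned analysis that ignores prohibited use does not close the gap, since it moves away from scoring these subjects as failures.

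**Conclusion.** The point holds as a defect in the endpoint definition. For non-study IVIG it is clear on the text: unless given within another experimental study, its use is not a failure by any rule, and the subject can be a Day 7 or Day 14 success. For anti-interleukin agents the scoring is unspecified, and the protocol and SAP wordings that would guide the blinded review differ.

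The size is unknown. If uncounted rescue is commoner on placebo, the difference is diluted; 65% vs 81% would cost about 16 points of power at 88 per arm (83.1% to 66.9%) and about 15 at 104 (88.8% to 74.2%). Equal rescue leaves the 20-point difference intact, and more rescue on IVIG inflates it. All of these rest on assumed rates. The case for acting does not depend on a particular rate: classification of a confirmatory endpoint should not turn on later judgement about which drugs the rule meant.

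**What to change.** Reconcile Protocol 4.1.2 (exclusion 11), 4.2, 4.3.1 and 9.2.3.2 with SAP 13. Which treatments should be clinically forbidden is for the sponsor and investigators; this review takes no position.

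For endpoint scoring only:

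1. Name non-study IVIG and anti-interleukin agents in the list that triggers failure at Day 7 and Day 14, with one wording in both documents.
2. Apply that list to the unusable-date rules for discharge, ICU and IMV.
3. Fix the list before blinded review, so that the review applies it and does not define it.
4. Do not carry the wider list into the rule that removes prohibited-medication users from the severe-progression and mortality analyses. Keep these subjects and count their events. If rescue were commoner on placebo, a wider exclusion would drop more placebo subjects, plausibly the sicker ones, and could add bias.

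The analysis already planned regardless of prohibited medication then shows the other reading.

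The cost is wording in the two documents. The use is already recorded as concomitant medication, so no new data are needed. A few subjects may move to failure, so observed success rates may be slightly lower.
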